13.1 Statistical Analysis Data Set Definition

① Intentional analysis set (Intention-to-treat population)

All subjects who participated in randomization were included.

② Full analysis set (Full Analysis Set)

According to the principle of intention-to-treat analysis (ITT), all subjects who were randomized and who had received at least one post-treatment efficacy assessment were included.

③ Compliant with the scheme set (Per-protocol Set)

All patients who met the trial protocol, had good compliance (80%-120% of medication), did not use prohibited medication during the trial or completed the contents of the case report form.

④ Security Analysis Set (Safety Analysis Set)

All enrolled cases, all patients who have used the trial drug at least once and have safety records after drug use, belong to the safety analysis set. This dataset is used for safety analysis.

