4.3 Sample size calculation

This clinical trial adopts the sample size calculation formula of 2 groups of quantitative data.

$$n = \frac{(Z_{\alpha} + Z_{\beta})^2 * 2\sigma^2}{\delta^2}$$

Calculation formula:

n represents the sample size of each group.

Take α as 0.05, Z value as two-sided, $Z_{\alpha} = 1.96$; β as one-sided, take power (test power) as 0.8, $Z_{\beta} = 0.84$.

σ represents the difference between the standard deviations of the treatment group and the control group, which is about 9.58 according to previous observations; δ represents the difference of the mean, that is, the difference between the mean of the treatment group and the control group, which is 10; the loss to follow-up rate is 20%.

According to the formula for calculating the sample size, there were 19 subjects in each of the experimental group and the control group, and a total of 38 subjects were included.

5. Subject recruitment

A total of 38 middle-advanced primary PD patients and controls who met the requirements in the inpatient or outpatient department of neurology of Zhujiang Hospital were continuously recruited.

6. Research subjects

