6.4 Exit criteria

- (1) Subjects should withdraw from the trial when they have abnormal vital organ function, allergic reactions to drugs, poor compliance, exacerbation of the disease, or serious adverse reactions that need to stop the treatment of the trial drug or use other treatment methods;
- (2) Subjects who are ineffective, cannot tolerate adverse reactions, wish to take other treatment methods, or request to withdraw from the trial without any reason.

7. Research Interventions

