13.2.6 Effectiveness Analysis

① **Primary endpoint:** Modified MDS-UPDRS scale score

Measurement data were expressed as mean \pm standard deviation ($\bar{x} \pm s$). For those with normal distribution and homogeneous variance, paired-samples t-test was used for intra-group comparison, two independent samples t-test was used for inter-group comparison, and t' was used for unequal variances. test. $P < 0.05$ was considered to be statistically significant.

② **Secondary endpoints:** NMSS scale, PDQ-39 scale, H&Y grade, LDE, 10M-WT, cerebrospinal fluid blood biomarkers, MRI+SWI changes

Measurement data were expressed as mean \pm standard deviation ($x \pm s$). For those with normal distribution and homogeneous variance, paired-samples t-test was used for intra-group comparison, two independent samples t-test was used for inter-group comparison, and t' was used for unequal variances. For skewed data, median + interquartile range ($m \pm Q$) was used, and nonparametric test was used; $P < 0.05$ was considered statistically significant.

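### If the primary t-test is made at one final visit, full-analysis-set patients who left earlier drop out of it and their recorded scores do not inform it

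*Protocol*

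**What the plan says.** - **Analysis sets (Protocol 13.1).** The intention-to-treat set holds everyone randomised. For the full analysis set, "all subjects who were randomized and who had received at least one post-treatment efficacy assessment were included". No efficacy analysis is tied to a named set.
- **Primary test (Protocol 13.2.6, item 1).** For the MDS-UPDRS score, "two independent samples t-test was used for inter-group comparison", with t' for unequal variances and a paired t-test within arms. No visit is named.
- **Missing data (Protocol 13.2.3).** A scale missed through force majeure is to be obtained within a week. For patients who withdraw or stop study treatment, the gaps may stay empty. No imputation method follows, although the heading announces one.
- **Scoring times.** The visit schedule and 8.3 score MDS-UPDRS at V2, V3 and V4 (weeks 4, 8 and 12). Section 10.1 also lists days within each treatment cycle.
- **Reasons to leave (Protocol 6.4, repeated in 9.1).** These include "Subjects who are ineffective, cannot tolerate adverse reactions, wish to take other treatment methods".
- **Expected loss (Protocol 4.3).** "the loss to follow-up rate is 20" per cent.

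**The concern.** A two-sample t-test takes one value per patient. A patient scored at V2 and V3 who leaves before V4 is a member of the full analysis set, yet has no value for a V4 test. The set and the test therefore do not fit each other wherever a single visit decides.

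The mismatch matters because leaving can depend on scores already recorded, lack of effect being an accepted reason to exit. If more poor responders leave one arm than the other, the patients still present at week 12 no longer form a fair comparison. A t-test on them can show a difference that is not there, or hide one that is. The V2 and V3 scores that could correct for this would be in hand but unused.

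The protocol itself fixes the sets, the test and the missing-data rule, so this is not just a detail left to a statistical analysis plan.

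**Working it through.** **1. Inputs from Protocol 4.3.** "Take α as 0.05, Z value as two-sided" (1.96); "take power (test power) as 0.8" (0.84); SD, "which is about 9.58 according to previous observations"; and "the difference between the mean of the treatment group and the control group, which is 10". Loss is 20%.

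**2. The plan's own figure.**
- n = (1.96 + 0.84)² × 2 × 9.58² / 10² = 7.84 × 2 × 91.7764 / 100 = 14.39, so 15 evaluable per arm.
- 15 / 0.8 = 18.75, so 19 per arm. This matches the stated 19 and 38.
- The sample size therefore already allows for about four patients per arm without a usable score (0.20 × 19 = 3.8).

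**3. Power for a 10-point difference (noncentral t).** With 19 per arm analysed it is 87.9%; with 15 per arm it is 78.8%. In simulation with four per arm lost at random after V3, the t-test has 79%. A likelihood analysis that also uses V2 and V3 has 81%, 83% and 85% at between-visit correlations of 0.5, 0.7 and 0.8.

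**4. Bias with no true effect.** The documents give no between-visit correlation and no pattern of loss. Both are assumed here: correlation ρ of 0.5, 0.7 or 0.8, SD 9.58, 19 per arm, and a higher score is worse.

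Suppose the k patients with the worst V3 scores leave an arm. The V3 mean of those who stay then falls by 9.58 × b(k), where b(k) is the sum of the k largest expected normal order statistics for n = 19, divided by 19 − k. The V4 mean falls by ρ times that.
- b(4) = (1.844 + 1.380 + 1.099 + 0.886) / 15 = 0.347
- b(2) = (1.844 + 1.380) / 17 = 0.190
- Four SGB, no control: 9.58 × 0.347 = 3.33; times ρ gives 1.7, 2.3 and 2.7 points.
- Four SGB, two control: 9.58 × (0.347 − 0.190) = 1.51; times ρ gives 0.8, 1.1 and 1.2 points.

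Simulation agrees to within about 0.1 point and supplies the error rates. Negative values favour SGB:

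| Who leaves after V3 | Bias at ρ = 0.5 / 0.7 / 0.8 | Two-sided error rate |
|---|---|---|
| 4 worst in each arm | about 0 | 6% to 7% |
| 4 SGB, 2 control, leaving only partly related to V3 | −0.5 / −0.6 / −0.7 | about 6% |
| 4 SGB, 2 control, worst scorers | −0.8 / −1.0 / −1.2 | 6% / 8% / 9% |
| 4 SGB, 0 control, leaving only partly related to V3 | −0.9 / −1.3 / −1.5 | 6% / 7% / 8% |
| 4 SGB, 0 control, worst scorers | −1.7 / −2.3 / −2.7 | 8% / 11% / 14% |
| 0 SGB, 4 control, worst scorers | +1.6 to +2.7 | as the row above, by symmetry |

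Partly related means log-odds of leaving of 1 per SD of V3. A heavier two-arm loss, the worst 30% of SGB against the worst 10% of control, gives −1.4 to −2.1 points at ρ of 0.5 to 0.7, with error 7% to 11%.

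**5. Using the earlier scores.** In the four-against-none case, a likelihood estimate that uses V2 and V3 has bias of about 0 and error of 4% to 5%. This is partly built in, because loss was simulated to depend only on a recorded score.

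**The case against.** A reader might infer that the protocol prescribes a completers-only analysis and discards early leavers' scores. It does not say so. No test visit is named, and separate t-tests at V2 and V3 would use those scores at those visits. What stands is narrower: any single-visit test omits full-set members who were not scored then.

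A reader might also infer that the plan favours SGB. The exit criteria apply to both arms, and nothing in the documents predicts loss in the SGB arm alone. Equal loss gives almost no bias, and loss from the control arm alone reverses its direction.

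Three further objections carry some weight:
- Section 9.3 requires an efficacy check at withdrawal, and the visit schedule allows an MDS-UPDRS score at exit when necessary. Some leavers may therefore have a final score, but no rule says how it enters the analysis.
- Section 13.2.3 can be read as a rule on data collection that does not forbid imputation, and a statistical analysis plan might add a method. As written, though, the protocol gives none and permits the gaps to stay.
- The case for more power is weak, because 20% loss is already in the sample size.

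**Conclusion.** The point holds conditionally. If a single final visit decides the primary comparison, the stated t-test does not analyse the full analysis set as 13.1 defines it, and V2 and V3 scores of early leavers do not inform the result. Against the planned difference of 10 points, the possible bias runs from about 0 (equal loss), through 0.5 to 1.5 points (milder imbalance, at most four leaving per arm), to 1.7 to 2.7 points in the extreme one-arm case. It can go in either direction. These figures rest on assumed correlations and loss patterns, so they show what could happen and do not forecast it. The likely gain in power is modest, from 79% to about 81% to 85%. The change is worth making because it is cheap and brings the primary analysis closer to the plan's own stated principle.

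**What to change.** In Protocol 13.2.6, item 1:
- Name the deciding visit and state that the primary comparison uses the full analysis set.
- Make the main analysis a mixed model for repeated measures on all V2, V3 and V4 MDS-UPDRS scores, with arm, visit and arm-by-visit effects and an unstructured covariance. Take the result from the arm contrast at the deciding visit. SPSS, already named in 13.2.1, fits this with its MIXED procedure.
- Keep the two-sample t-test on observed cases at that visit as a sensitivity analysis.
- Report by arm the patients with no post-treatment score. The model does not bring them in, so the full intention-to-treat set is still not analysed.

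The cost is slightly more analysis work, with no extra patients or visits. The model assumes that loss is explained by the recorded scores. That is weaker than what the t-test on remaining patients needs, but it is still an assumption. The model as described uses only the scheduled visits, so the scores within cycles listed in 10.1 stay outside it.

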7.1 Description of the research intervention

- (1) Interventions in the experimental group: standard antiparkinsonian therapy + stellate ganglion block.
- (2) Control group intervention: standard antiparkinsonian therapy.

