7.2 Dosage and start and end times

Test group: Oral standard anti-Parkinsonian drugs, including compound levodopa, pramipexole hydrochloride, ropinirole, entacapone, amantadine, antan, etc. A total of three cycles of stellate ganglion block were performed, with 10 stellate ganglion blocks per cycle (once a day), with a 20-day interval between the two cycles;

Control group: Oral standard antiparkinsonian drug

8. Research Process

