11.1 Definition

Adverse Event (Adverse Event, AE) :

- (1) Allergies: Subjects experienced anesthesia allergies during the planetary ganglion block therapy;
- (2) Nerve damage: Accidental nerve damage, transient upper limb numbness, and hoarseness during planetary ganglion block therapy;
- (3) Adverse reactions caused by local anesthetics: such as dizziness, chills, tinnitus, and anesthetics accidentally entering blood vessels during planetary ganglion block therapy;
- (4) Pneumothorax: the puncture needle accidentally penetrates the lung;

(5) Improper puncture site: Brachial plexus block, high epidural block, and subarachnoid block occur when the puncture site is improper.

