11.2 Adverse events/serious adverse events recording

All adverse events and serious adverse events that occurred during the trial, such as local anesthetic allergy, organ dysfunction, intolerance to operation, etc., regardless of whether they were causally related to the trial drug, should be recorded in the original records and case reports. in the table. Records of adverse events and serious adverse events should include:

- (1) Event name;
- (2) The duration of the event, including the time of occurrence and the time of its end;
- (3) The severity of the incident;
- (4) Judgment of the causal relationship between the event and the research product;
- (5) Take measures; if treatment is required, record the treatment methods and medications given;
- (6) The outcome of the event;
- (7) The researcher should sign and sign the date.

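### Section 13.1 contains two incompatible safety sets, and the adverse-event definition in 11.1 is narrower than 11.2 and the visit table, so control-arm events can be left out of the safety analysis

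*Protocol*

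**What the plan says.** Section 13.1, item ④, gives the safety set in one sentence. It opens with every enrolled case and then names a narrower group: "all patients who have used the trial drug at least once and have safety records after drug use". The next sentence assigns safety analysis to this set.

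The arms are set out in section 7.1. One reads "Interventions in the experimental group: standard antiparkinsonian therapy + stellate ganglion block"; the other reads "Control group intervention: standard antiparkinsonian therapy". Section 7.2 repeats for the controls: "Control group: Oral standard antiparkinsonian drug". The block is the only component that one arm receives and the other does not.

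Section 11.1, headed as a definition, lists five kinds of adverse event. The first is typical: "Allergies: Subjects experienced anesthesia allergies during the planetary ganglion block therapy". Section 11.2 then requires adverse events and serious adverse events during the trial to be recorded "regardless of whether they were causally related to the trial drug". The visit table marks adverse events at every visit, with no restriction by arm. The safety analysis section (numbered 15.2.7, within section 13) describes event types, their frequency and their relation to the trial drug, and does not mention arms.

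**The concern.** Background illness in this population (Hoehn-Yahr 3 to 5) can itself produce worsening, admissions and drug effects over three months of treatment. In an open-label trial, judging whether such an event came from the block is exposed to bias. The safeguard is the rate of the same events in patients followed concurrently without the block.

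Two pieces of wording put that safeguard at risk. One makes safety-set membership depend on using an undefined trial drug. The other defines an adverse event by a list that a control patient cannot meet through the trial treatment. Someone applying both literally would produce a one-arm list of procedure complications, although the trial also follows a control arm and marks adverse events at its visits.

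**Working it through.** **Number of patients involved.** Section 4.3 gives σ = 9.58, δ = 10, Zα = 1.96, Zβ = 0.84 and 20% loss to follow-up.

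- n = 2σ²(Zα + Zβ)²/δ² = 2 × 9.58² × 2.80² / 10² = 14.39, rounded up to 15 per arm.
- Allowing for loss: 15 / (1 − 0.20) = 18.75, rounded up to 19 per arm, 38 in total.

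The plan's own figure is reproduced. Allocation is 1:1 within two age strata (section 4.2), so each arm has about 19 patients.

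**Size of the safety set under each reading of 13.1 ④.**

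| Reading | Block arm | Control arm | Share of the 38 left out |
|---|---|---|---|
| All enrolled cases | 19 | 19 | 0/38 = 0% |
| Trial drug means the block | up to 19 | 0 | about 19/38 = 50% |
| Trial drug includes the oral standard drugs | up to 19 | up to 19 | none by arm |

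The counts in the last two rows also depend on a safety record after first use.

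**Which reading fits the rest of the protocol.** Three places point to the block.

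- Section 11.5 treats the antiparkinsonian drugs as the basic medication and names the block separately.
- Sections 11.2 and 15.2.7 judge causality against the trial drug or research product. If that meant the standard drugs, which both arms take, the assessment would not address the block.
- Sections 6.4 and 9.1 contrast the trial drug with other treatments.

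Two places point the other way.

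- The per-protocol set, also in 13.1, uses an 80%–120% medication-intake rule, which fits oral therapy in both arms.
- The exit and discontinuation criteria (6.4, 9.2) use trial or study drug for subjects in general.

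The block is the more natural reading, but it is not stated.

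**Adverse-event scope, side by side.**

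- 11.1: five items, namely allergy to the anaesthetic during the block, nerve injury during the block, local-anaesthetic reactions during the block, pneumothorax from the needle, and a misplaced puncture. All 5 of 5 are tied to the procedure.
- 11.2: all events during the trial, whatever the cause. It gives three examples. Two relate to the anaesthetic or the operation; the third, organ dysfunction, is not among the five items of 11.1.
- Visit table: adverse events at every visit, including screening on Day −1, before any block could be given.
- 11.3.1: severity grades that cover admission to hospital, disability and death, which goes beyond the 11.1 list.

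So 11.1 is narrower than 11.2, 11.3.1 and the visit table, and the protocol does not say which governs.

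**The case against.** The strongest reply is that the protocol nowhere says controls are excluded. The safety-set sentence begins with all enrolled cases, and the English reads like a translation, so a categorical exclusion should not rest on one noun. This stands. A reader might infer that the control arm simply drops out of the safety set; the text supports only that it can, on the most natural reading of an undefined term.

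The reply also stands on collection. Section 11.2 does not refer back to 11.1, so a reader who infers that its recording duty is limited to the five listed items goes beyond the text. With the visit table, it means that control-arm events should be recorded. Nor is a safety comparison planned: section 15.2.7 is descriptive, and table layout is commonly left to a statistical analysis plan.

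What does not stand is the conclusion that nothing needs changing. The protocol itself fixes the safety set and the definition, so neither is merely detail left for later. Collected events do not help if the patients who had them are outside the only set assigned to safety analysis. A purely descriptive table by arm still needs controls in that set.

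**Conclusion.** The point holds as an internal contradiction with a practical consequence. The safety population is 38 or about 19 depending on how one sentence is read. Under the trial-drug condition, taken as the block, about half of the randomised patients are outside it, all of them controls. Separately, 11.1 conflicts with 11.2 and the visit table over what counts as an adverse event.

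The 50% figure assumes full recruitment of 38, 1:1 allocation, the block as the meaning of trial drug, and no control patient receiving a block. The documents give no adverse-event rate, so the consequence cannot be expressed as a frequency. The precision of the block arm's own rate would be the same after the fix; what the fix secures is the concurrent control rate.

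A secondary documentation point: the protocol gives no definition of a serious adverse event, although 11.6 attaches reporting duties to the term. The severity grades in 11.3.1 overlap with usual seriousness criteria but do not replace a definition.

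**What to change.** - **13.1 ④:** define the safety set as all randomised patients, analysed by the treatment actually received (at least one block versus none). Remove the condition on the trial drug, or define that term once and use it consistently.
- **11.1:** define an adverse event as any untoward medical occurrence after randomisation in either arm. Keep the five listed complications as events of special interest. Add a definition of a serious adverse event.
- **Safety analysis section (15.2.7):** state that events are described by arm, grouped as in the revised 13.1 ④.

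The cost is wording only. The visit table already collects adverse events at every visit, so no visit is added, and the 19 per arm does not change. The case report form should be checked to confirm that it accepts any event in either arm.

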13.2 Statistical Analysis Program

13.2.1 Statistical analysis software

Statistical analysis was performed using SPSS 25.0 statistical software.

13.2.2 Basic Principles of Statistical Analysis

All statistical inferences were two-sided tests, the test level for statistical significance was set at 0.05, and the confidence intervals for parameters were estimated using 95% confidence intervals. The parametric method should be used as much as possible. When the data does not meet the conditions of the parametric method, the data conversion method can be used to make it meet the conditions. If it still does not meet the conditions, the non-parametric method can be considered.

13.2.3 Missing data imputation

If the patient fails to complete the corresponding scale or CRF due to force majeure factors, it should be completed within one week of missing data; if the patient withdraws from the study or terminates the study treatment, the corresponding missing data need not be completed.

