9.1 Withdrawal Criteria

Reasons for a subject to withdraw from the study may include:

Subjects should withdraw from the trial when they have abnormal vital organ function, allergic reactions to drugs, poor compliance, exacerbation of disease or serious adverse reactions that require stopping the treatment of the trial drug or using other treatment methods;

Subjects who are ineffective, cannot tolerate adverse reactions, wish to take other treatment methods, or request to withdraw from the trial without any reason.

Subject withdrew informed consent and refused further follow-up;

Subjects lost to follow-up;

Subject died.

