9.2 Criteria for discontinuation of study treatment

Criteria for subjects to discontinue study treatment are as follows:

(1) Subjects withdrew their informed consent for any reason or no reason and refused to continue receiving study drug treatment;

(2) According to the judgment of the investigator, the subject's clinical symptoms have deteriorated/physical condition has decreased, the study endpoint has been reached, or there are intolerable side effects, including any abnormal clinical or laboratory tests or other medical conditions;

(3) Other circumstances that the investigator deems necessary to terminate the study drug treatment;

(4) The sponsor terminated the study.

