9.3 Steps to withdraw from the study or discontinue study treatment

Subjects must be checked for efficacy and safety in accordance with the protocol for withdrawal from the study and final observation and follow-up, and AEs and outcomes must be fully recorded. The researcher can suggest or provide alternative treatment methods to the subjects according to the actual situation of the subjects.

If the subject refuses to come to the research center for further visits, their survival status should continue to be tracked unless the subject withdraws informed consent. In this case, no further study evaluations should be conducted and no further data should be collected.

10. Evaluation indicators

10.1 Primary endpoint: Modified MDS-UPDRS scale score (the revised version of the Movement Disorders Association Unified Parkinson's Disease Rating Scale, which has four main parts, including both physician and patient aspects, the first part is psychological, behavioral and emotional; the second Part is activities of daily living; the third part is motor symptoms; the fourth part is complications), SGB is carried out in three cycles, each cycle is carried out for 6-10 days, and the interval between each cycle is 20 ± 7 days; The first, second, and third cycles of Day0, Day5, and the last day were measured and recorded.

10.2 Secondary endpoints : NMSS (Non-motor Symptom Evaluation Scale), PDQ-39 (Self-rating scale for clinical evaluation of the quality of life in patients with Kinson's disease), H&Y classification (Classification of Parkinson's disease), LDE (levodopa equivalent dose), 10M-WT (10m walk test), cerebrospinal fluid and blood biomarkers, SGB were carried out for a total of three cycles, each cycle was carried out for 6-10 days, and the interval between each cycle was 20 ± 7 days; On Day0, Day5, and the last day of the third cycle, the scale data were measured and recorded. The researchers performed head MRI + susceptibility-weighted imaging on Day 0 of the first cycle and Day 10 of the third cycle, respectively, to compare the changes in the "swallowtail sign" of two successive head MRIs.

11. Adverse events, serious adverse events, adverse reactions

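### Section 9.3 requires an efficacy check at exit, but the visit schedule makes the exit MDS-UPDRS optional, and nothing expressly requires it at the remaining visits once a patient stops or leaves

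*Protocol*

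**What the plan says.** **Reasons to leave or stop.** Section 9.1 states: "Subjects should withdraw from the trial when they have abnormal vital organ function, allergic reactions to drugs, poor compliance, exacerbation of disease". Sections 6.4 and 9.1 also list "Subjects who are ineffective, cannot tolerate adverse reactions, wish to take other treatment methods" as leaving the trial. Section 9.2, on stopping study treatment only, includes the investigator's judgement that "clinical symptoms have deteriorated/physical condition has decreased, the study endpoint has been reached, or there are intolerable side effects".

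**What happens at exit.** Section 9.3, headed for both withdrawal and discontinuation of treatment, states: "Subjects must be checked for efficacy and safety in accordance with the protocol for withdrawal from the study and final observation and follow-up". It then provides for tracking of survival status when a patient refuses to come back. It bars further evaluation and data collection in a case that can be read as refusal or as withdrawn consent.

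**Visit schedule.** In the exit column, vital signs, physical examination and adverse events carry an asterisk. The MDS-UPDRS and the secondary scales are marked as conditional on need.

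**Missing data.** For a scale or form missed for reasons beyond the patient's control, 13.2.3 says "it should be completed within one week of missing data". The same sentence continues: "if the patient withdraws from the study or terminates the study treatment, the corresponding missing data need not be completed".

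**Analysis.** Section 13.1 defines an intention-to-treat set of everyone randomised, and a full analysis set that needs at least one efficacy assessment after treatment. Section 13.2.6 compares the arms on the MDS-UPDRS with two-sample t-tests.

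**The concern.** The primary endpoint is a rating that exists only if someone takes it. A site that follows the exit column and 13.2.3 literally can let a patient who stops for lack of effect or worsening go without an exit score and without scores at the remaining visits, and still be within protocol. Several of the listed reasons are themselves poor outcomes, so such gaps would not be random with respect to the MDS-UPDRS.

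The between-arm t-tests would then describe those who stayed rather than all who were randomised. A patient who leaves before the first post-treatment score could also fall out of the full analysis set. The SAP can choose a model and sensitivity analyses, but it cannot restore scores that were never taken. Whether they are taken is settled by the protocol.

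**Working it through.** **1. The sections side by side**

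| Question | Where | Answer |
|---|---|---|
| Is efficacy checked at exit or treatment stop? | 9.3 | Yes, mandatory; scale not named |
| Is the MDS-UPDRS taken at the exit visit? | Visit schedule, exit column | Only as needed |
| Are there visits after exit? | 9.3 | Implied, unless the patient refuses |
| Is the MDS-UPDRS scored at those visits? | No section | Not stated |
| Must missing data be completed after exit? | 13.2.3 | No, and the same after merely stopping treatment |
| Is worsening a withdrawal or a treatment stop? | 9.1 and 9.2 | Listed under both |

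Rows 1 and 2 conflict. Row 4 is a gap, and row 5 can be read as permission to leave it open.

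**2. The plan's own figure**

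Inputs from 4.3: two-sided alpha 0.05 (Z 1.96), power 0.8 (Z 0.84), SD 9.58, difference 10, loss 20%.

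- n = (1.96 + 0.84)² × 2 × 9.58² / 10² = 7.84 × 2 × 91.78 / 100 = 14.39, rounded up to 15 per arm.
- 15 / (1 − 0.20) = 18.75, rounded up to 19 per arm, 38 in total.

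The stated 19 per arm reproduces. With 15 per arm left, power is 81.6% by the normal approximation and 78.8% by the t-test. The 20% allowance therefore covers the loss of precision. It gives no protection if the loss depends on outcome.

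**3. Illustration of the possible bias**

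The protocol gives no rate of exit for poor outcome, so what follows rests on assumptions: no true effect, SD 9.58, 19 per arm, lower score better, no leaver's score used, pooled two-sided t-test at 0.05. Section 14.3 aims for dropout within 20%. 0.20 × 19 = 3.8, taken as 4 per arm (4/19 = 21%, slightly above that ceiling). The 4 patients are the worst-ranked on an exit variable whose correlation with the score is r, or are lost at random. Each setting was simulated 100,000 times, so the simulation error on a rate of 0.05 is √(0.05 × 0.95 / 100,000) = 0.0007.

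| r | Bias, outcome-related in one arm, random in the other (points) | Type I error, one arm | Type I error, both arms outcome-related (bias about 0) |
|---|---|---|---|
| 0.2 | 0.67 | 0.054 to 0.055 | 0.051 |
| 0.3 | 1.01 to 1.02 | 0.060 | 0.053 |
| 0.5 | 1.65 | 0.080 | 0.057 |
| 0.7 | 2.33 | 0.111 to 0.113 | 0.066 |
| 1 | 3.33 | 0.195 | 0.101 |

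Bias is close to r × 3.33 (0.2 × 3.33 = 0.67; 0.3 × 3.33 = 1.00). It favours whichever arm loses its poor responders, and the figures mirror each other when the arms are swapped. Random loss in both arms gives bias of about 0 and a rate of 0.050.

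Two milder settings, outcome-related in one arm only:

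- 2 lost per arm: about 0.4 points and a rate of 0.051 to 0.053 at r = 0.2; 1.8 points and about 0.10 at r = 1.
- 4 leavers per arm, of whom a random 2 are scored anyway (SGB arm outcome-related): 0.3 points and 0.051 at r = 0.2; 1.5 points and 0.078 at r = 1.

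**The case against.** Three stronger readings are tempting, and the protocol supports none of them.

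*Patients who leave are never scored.* Section 9.3 makes an efficacy check mandatory after withdrawal and after treatment stop. It falls back to survival status only when the patient refuses visits, so other leavers are expected to return. The natural reading of 13.2.3 is also narrower: its first half sets a one-week make-up of missed forms, and its second half may only lift that duty. Not requiring data is also not the same as forbidding them. All of this stands. What remains is that 13.2.3 does not say its waiver is so limited, and that neither 9.3 nor any other section expressly asks for the MDS-UPDRS at the later visits.

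*The visits themselves end when SGB ends*, because 8.3 speaks of treatment visits and 10.1 ties the score to days of SGB cycles. This does not hold. V2 to V4 are calendar visits at 4, 8 and 12 weeks, and they apply equally to controls, who never receive SGB. The synopsis also has monthly part III scores after treatment. Stopping SGB does not remove the visits.

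*The design favours SGB.* The exit rules cover both arms. Open allocation, and procedure-related events that can arise only with SGB, make unequal loss plausible. They do not show which arm would lose more of its poor responders.

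It is also fair to say that the large figures need one-sided loss tied almost perfectly to the score, and that the 20% includes refusals, losses to follow-up and deaths, which no wording can recover.

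**Conclusion.** The point holds as an inconsistency and a gap in data collection. Section 9.3 and the exit column disagree on whether efficacy is assessed at exit, 13.2.3 puts a mere treatment stop on the same footing as withdrawal, and scoring at the remaining visits is nowhere expressly required. Because the listed exits include poor outcomes, gaps in the primary endpoint can depend on outcome.

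No figure in the plan is wrong. Under the assumptions above, the consequence runs from none (loss alike in both arms), through small (weak correlation, one arm), to about a third of the planned 10-point difference (3.33 / 10) in the extreme case. The documents do not say where in that range the trial would fall. This is a change that should be made because it is cheap and cannot be made afterwards. It is not evidence that the result will be biased. Confidence is medium.

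**What to change.** Leave the clinical criteria for stopping or leaving as they are. Reconcile 6.4, 9.1, 9.2, 9.3, 13.2.3 and the exit column on data collection only:

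- Make the MDS-UPDRS a required item in the exit column, in line with 9.3.
- State that patients who stop treatment or exit for any reason, and who have not refused visits or withdrawn consent, are still scored at the remaining scheduled visits (V2 to V4).
- Limit the waiver in 13.2.3 to the one-week make-up of missed forms.
- State that every observed score of all randomised patients is used, as allocated. Leave the model and sensitivity analyses to the SAP.

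The cost is protocol wording and a few already scheduled visits for patients off treatment. The sample size does not change. The estimate may come out less favourable, because poor responders stay in it.
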